This research will be done in three phases involving young adults, ages 18-34, susceptible to WTS (i.e., nonusers who do not oppose trying WTS)²⁷ or engage in WTS at least monthly. Phase 1 concerns selecting text and graphic health warnings that can strongly influence beliefs and feelings about personal risk and intention to quit or try WTS. We will create, refine, and select text and graphic health warnings in four domains: 1) longer-term health effects, 2) shorter-term health effects, 3) addictiveness, and 4) types and levels of toxicant exposures. We will also select the most appealing waterpipe product and social allure ads themes that entice young adults to engage in WTS. The top two text and graphic health warnings in each domain and the top two product and social allure ads within each theme will be used for Phase 2. In Phase 2, using the online consumer crowdsourcing platform Turkprime²⁸, susceptible nonsmokers and smokers (N=1000 per group) will be randomized to review ads with: 1) no health warnings, 2) text only health warnings, or 3) text + graphic health warnings. Nested within Arms 2 and 3 is health warning domain and ad theme. Reactions to ads will include ability to grab attention, cognitive and affective beliefs and attitudes toward each ad and ad appeal to engage in WTS. Main outcomes will include perceived risk and worry about harms (i.e., risk appraisal), attitudes

toward WTS, and intention to try or quit WTS. At a two-week follow-up, we will reassess these main outcomes, WTS, and recall of ad content. In Phase 3, using a new sample of susceptible nonsmokers and waterpipe tobacco smokers (N=100 per group), we will conduct an eye-tracking laboratory study to examine whether warnings evoke changes in attention that mediate changes in risk attitudes. The *primary aims* are to:

AIM 1 (Phase 1): Develop, pilot test, and select text and graphic health warnings in four domains (i.e., long/short-term health effects, addiction, type and level of toxicant exposures) that most dissuade WTS as well as select waterpipe tobacco product ads (themes of flavored tobacco, waterpipe apparatus) and social allure ads (four themes of eroticism, exoticism, social acceptance, and occasion appropriate) that most entice WTS.

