theme selected by each panel. Ads will be counterbalanced in a Latin-square design. For waterpipe product ads, participants will be randomized to review either the four tobacco- or four waterpipe apparatus-themed ads counterbalanced in a Latin-square design. Reactions to the social allure and waterpipe product ads will mirror those of the warnings. These will include: extent ad grabbed attention⁹⁶, credibility, relevance, fear appeal, extent ad influenced cognitive and affective beliefs about WTS¹⁰⁰, global attitude about ad⁹⁹, effort reviewing the ad, and extent ad *enticed* them to want to smoke (average of 2 items about ad making WTS more appealing and making them want to smoke 1=none at all, to 7=a great deal). They will rate extent each ad captured the social allure/product themes. Responses will be averaged for each ad within theme. *The top two ads within each social allure theme (8 total), and the top two within each product ad theme (4 total), with the highest mean score on enticing them to “want to smoke” waterpipe will be chosen for Phase 2.* All 24 ads will be used as stimuli for Phase 3.

Phase 2 Procedures:

Tests of ads with or without health warnings. Using Turkprime, we will recruit online 1000 waterpipe tobacco smokers and 1000 susceptible nonsmokers (\$2.00 payment). After screening and collecting baseline demographic and tobacco use data (e.g., cigarettes), participants will be stratified and randomized to review ads with or without health warnings. After obtaining participants' reactions to ads, we will assess key study constructs. All participants will complete a two-week follow-up.

Interventions. Participants will be stratified by sex and use of other tobacco products (no/yes) and then randomized in a 1:2:2 ratio to one of three arms: 1) no health warnings (i.e., review ads only – control); 2) text health warnings only; or 3) text + graphic health warnings. Nested within Arm 2 and 3 will be both ad themes (six total) and health warning domains (four total). Each arm is discussed below.

- *Control arm (N = 200).* Participants will be randomized with equal probability to one of the six ad themes (2 from product, 4 from social allure). They will view in counterbalanced order the two ads chosen for that theme from Phase 1 – no order effects are expected. They will not receive any warnings. (N ≈ 33 per cell).

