- *Text only health warnings (N = 400).* Ad theme selection will occur as with the control arm. Nested also as a between-subjects factor will be warning domain. Participants will see two text warnings from the same domain randomly assigned to the two ads within the same theme with ad order counterbalanced. Hence, this arm is primarily a 4 (warning domain: long-/short-term health effects, addiction, toxins) X 6 (ad theme: eroticism, exoticism, social acceptance, occasion appropriate, (flavored) tobacco, waterpipe apparatus) X 2 (ad order: A1A2 vs A2A1) between-subjects factorial design. Expecting no order effects, there are 24 main cells (N ≈ 32 per cell combining populations).
- *Text plus graphic health warnings (N = 400).* This arm is procedurally identical to the text only arm. The exception is that the two graphic warnings would be randomly added to the text warning in the same domain; thus, graphs are matched to the text warnings by health domain. (N ≈ 32 per cell combining populations).

Post intervention assessments. We will assess participants' reactions to each ad. *We will not assess reactions to warnings specifically; doing so may unduly bring attention to them.*

Reactions to warnings will have been obtained from Phase 1 and 3. After responding to the last ad, and aligned with the Message Impact Framework⁷², we will assess participants' knowledge of harms¹⁰², risk appraisals¹⁶, cognitive and affective beliefs and attitudes about WTS100, and intentions to quit/willingness to try WTS (4-item scale)¹⁴. We've used versions of these measures with $\alpha > .70$.

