Two-week follow-up. Using Turkprime, all participants will be asked to take an online survey two weeks later (\$2.00 payment). As *secondary aims*, the goal of the follow-up is to assess WTS and recall of ad content, both reactions to warnings⁷², and sustainability of earlier effects. A two-week time frame aligns with other studies on recall of warning labels⁵⁷. Participants will be asked first about their risk appraisals, cognitive and affective beliefs and attitudes about WTS, intention to quit/willingness to try WTS, and among smokers, frequency of WTS during the last two weeks. If a participant has not quit, they will be asked why. If a susceptible engaged in WTS, we will ask why. We will ask all if they saw and responded to WTS ads during the last two weeks (if yes, where), attended social events involving WTS or bought any WTS products – all no/yes. All will be asked to recall content of the two ads they viewed earlier. Analyses of recall will follow the steps by Strasser et al. on cigarette warnings¹⁰³. Based on an MTurk study that used similar methods as proposed¹⁰⁴, we expect 60% - 70% of participants will complete follow-up. We predict stronger sustainability of earlier effects and a higher percent of recall accuracy for warnings in the text + graphic arm than text only arm.

Phase 3 Procedures:

Participants will be stratified by sex and use of other tobacco products (no/yes) and then randomized in a 1:2:2 ratio to the three arms as Phase 2 (control, ads with text warnings, ads with text + graphic warnings). Tasks will be presented (and eye position sampled) using a Tobii T60XL eye tracker, which uses an unobtrusive infrared camera system to sample gaze position at 60 Hz (and with resolution <1 degree of visual angle) while allowing participants free head movement. Each image will be displayed for a fixed time of 10 seconds, during which participants move their head and eyes naturally while looking at the image. The images will consist of the 24 ads, 16 text and 16 graphic warnings from Phase 1. Details of each arm follows.

- *Control arm:* Participants will view the 24 ads from Phase 1 twice in random order without warnings. Further, 16 control non-tobacco ads matched for graphical content, presence of text, people, and other factors will be randomly distributed among these ads.

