We will use 90% power at .01 level of significance (two-tailed) for univariate tests and contrasts. Possible covariates obtained within the survey will include: race, sex, education, use of other tobacco products and among smokers, WTS frequency and level of addiction to WTS. Missing data will multiply imputed¹⁰⁵ as appropriate after checking missing randomness¹⁰⁶. For H2A and H2B, factorial MANOVAs will be conducted using SAS Proc GLM for all outcomes simultaneously. For H2A, if the omnibus multivariate test is significant at a .05 level, rather than .01, for the primary outcomes (risk appraisals, beliefs/feelings about WTS, global attitude about WTS, and intention to quit/willingness to try WTS), we will perform post-hoc univariate tests for each outcome at a .01 level for comparisons among: (a) ads without health warnings (control arm), with text warning only, and with both text + graphic health warnings; (b) four health warning domains; (c) six ad themes; d) two study populations; and interactions of a-d. Noteworthy, the interactions will be incomplete due to lack of health warnings in the control arm. Thus, Type IV sum of squares will be used to address empty cells. For H2B, the same statistical methods will be conducted as with H2A, using reactions to ads as the main outcomes. For H3, we have several mediators (reactions to ads). We will use the SAS Macro by Preacher and Hayes¹⁰⁷ to test multiple mediation effects in each study population. This approach address both multiple mediators simultaneously as well as multi-categorical variables¹⁰⁸ such as warning domains as proposed herein.

Importance / Value:

Waterpipe tobacco smoking (WTS) is becoming widespread in the United States among young adults^{17,18}. Increases in WTS are partly due to advertisements (ads) that entice young adults to engage in WTS^{19,20}. Often devoid of health warnings^{22,23}, waterpipe product and social allure ads likely mislead young adults to believe WTS is safe, promoting experimentation with WTS and reducing the desire to quit among users^{19,24}. Thus, as shown with cigarette health

warnings¹, designing effective text and graphic (i.e., pictorial) warnings is vital to curbing the effects of these ads.

Risks / Benefits:

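### Waterpipe status is not a randomisation stratum, so the 1:2:2 split is not guaranteed within smokers or within susceptible nonsmokers; the cost is small in Phase 2 and conditional in Phase 3

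*Combined protocol and SAP*

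**What the plan says.** Phase 2 Procedures, under Interventions, gives the allocation rule: "Participants will be stratified by sex and use of other tobacco products (no/yes) and then randomized in a 1:2:2 ratio" across the three arms. Phase 3 Procedures repeats it: "Participants will be stratified by sex and use of other tobacco products (no/yes) and then randomized in a 1:2:2 ratio to the three arms as" in Phase 2. Neither sentence mentions waterpipe status.

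Elsewhere the plan treats the two populations as part of the design:

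- Study Design, on Phase 2: "susceptible nonsmokers and smokers (N=1000 per group) will be randomized to review ads with" one of three warning conditions.
- Phase 2 Procedures sizes the arms as "Control arm (N = 200"), "Text only health warnings (N = 400"), and another 400 for text plus graphic.
- The section on sample size and statistical considerations makes population a crossed factor in the power calculation and a factor, with interactions, in the H2A and H2B MANOVAs. For H3 it uses a macro to "test multiple mediation effects in each study population".

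For Phase 3, Study Design gives only the recruitment figure: "susceptible nonsmokers and waterpipe tobacco smokers (N=100 per group"). No Phase 3 arm sizes are stated. The statistical section describes analyses for H2A, H2B and H3 but none for Aim 4, the eye-tracking aim.

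**The concern.** A randomiser programmed literally from the two allocation sentences would have four strata (sex by other tobacco use). With blocking inside those strata, it would hold the arm totals close to 1:2:2 over everyone, but the split among smokers and the split among nonsmokers would be left to chance. Other tobacco use does not stand in for waterpipe status, because members of either population may answer yes or no.

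Two things could suffer. A contrast made inside one population could have fewer controls than planned, and control is already the smallest arm. A pooled contrast that ignored population could compare arms with different proportions of smokers.

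**Working it through.** **1. Are the stated arm sizes per population?** Applying 1:2:2 to 1000 gives 1000 × 1/5 = 200 and 1000 × 2/5 = 400 twice, which matches the plan. Applied to 2000 it would give 400, 800 and 800. The cell counts agree: 200/6 = 33.3 for control (plan: about 33), and 2 × 400/24 = 33.3 for a warning cell with populations combined (plan: about 32). So 200/400/400 are per-population figures. The same ratio applied to 100 implies 20/40/40 per population in Phase 3.

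**2. Is population built into the power calculation?** The design is 3 × 4 × 6 × 2 = 144 cells, and the largest interaction has 2 × 3 × 5 × 1 = 30 degrees of freedom. With noncentrality N·f², α = 0.01 and 90% power, the required totals come to 3934, 657 and 289, exactly as stated. The present point does not change them.

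**3. Controls per population if only pooled arm totals are fixed.** The number of smokers among c controls drawn from N people, half of them smokers, is hypergeometric, with SD = √[c × ½ × ½ × (N − c)/(N − 1)].

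| Phase | N | c | Mean | SD | 95% range |
|---|---|---|---|---|---|
| 2 | 2000 | 400 | 200 | √(400 × 0.25 × 1600/1999) = 8.9 | 182–218 |
| 3 | 200 | 40 | 20 | √(40 × 0.25 × 160/199) = 2.8 | 14–26 |

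In Phase 3 the chance of a 16:24 split or worse is 22%. If arm totals were not fixed at all (simple randomisation), the binomial SDs are √(1000 × 0.2 × 0.8) = 12.6 and √(100 × 0.2 × 0.8) = 4.0, with ranges 176–225 and 12–28.

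**4. Do the listed strata help?** I simulated Phase 3 with blocks of 5 inside sex by other tobacco use. Block size and tobacco-use rates are assumptions. With other tobacco use at 70% in smokers and 40% in nonsmokers, the SD is 2.7; at 80% and 20% it is 2.3. The range is 15–25 in both cases, so they help only slightly.

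**5. Effect on a control-versus-text contrast inside one population.** The standard error in SD units is √(1/n₁ + 1/n₂). The people not in control are split evenly between the two warning arms. Power is two-sided at α = 0.01 (noncentral t), and the effect sizes d are assumptions.

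| Phase, d | n₁ vs n₂ | SE | Power |
|---|---|---|---|
| 2, d = 0.3 | 200 vs 400 | 0.0866 | 81% |
| 2, d = 0.3 | 182 vs 409 | 0.0891 (+3%) | 78% |
| 2, d = 0.3 | 218 vs 391 | 0.0845 | 83% |
| 3, d = 0.8 | 20 vs 40 | 0.274 | 60% |
| 3, d = 0.8 | 14 vs 43 | 0.308 (+12%) | 48% |
| 3, d = 0.8 | 26 vs 37 | 0.256 | 68% |

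**6. Effect on a pooled, unadjusted Phase 3 contrast.** The difference in smoker share between control (40) and text (80) has SD √[0.25 × (200/199) × (1/40 + 1/80)] = 0.097, so a 95% range of about ±1.96 × 0.097 = ±19 percentage points. If smokers and nonsmokers differed by an assumed 1 SD on an outcome, a 19-point gap would shift the contrast by 0.19 SD.

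**7. With waterpipe status as a stratum.** The same simulation gives an SD of about 0.8 and 95% ranges of 199–201 in Phase 2 and 19–21 in Phase 3.

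**The case against.** The best reply is that the plan may already intend separate randomisation. Study Design speaks of each group of 1000 being randomised, recruitment is by fixed quota, and the arm sizes add up to exactly 1000. The documents mention neither blocks nor a single pooled list. This reading is possible and cannot be ruled out. It has to be inferred from arithmetic, however, while the sentences that define the procedure list the strata and leave this one out. If separate randomisation is intended, one line would record it.

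Second, stratification is not required for valid subgroup analysis. A comparison inside one population cannot be confounded by population, and the Phase 2 MANOVAs include population as a factor. This stands. When one population falls short of controls, the other gains them. A reader might infer that Phase 2 results would be biased; the documents do not support that.

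Third, a reader might infer that the defect is established as most serious in Phase 3, because the numbers are smallest there. But the per-population arm sizes and the by-population mediation are both stated for Phase 2 only: the mediators in H3 are reactions to ads, which is Aim 3. The Phase 3 figures describe a possible consequence and do not show a conflict within the Phase 3 text. Nor do the documents say that waterpipe status is the strongest predictor of the outcomes, and this point does not rely on it.

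**Conclusion.** The point holds in a limited form. As written, the allocation rule in both phases does not guarantee 1:2:2 within each population, while the Phase 2 arm sizes and the H2 and H3 analyses are framed by population.

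In Phase 2 the consequence is a small loss of precision: a standard error about 3% larger and about 3 points of power at the unfavourable end of the range, assuming d = 0.3 and fixed pooled totals. In Phase 3 the relative imbalance could be larger, but its importance is conditional. It would matter if results are analysed by population, or pooled without a term for it. Since no Aim 4 analysis is specified, the documents settle neither. The sample-size totals are unaffected, and nothing here invalidates the trial. The change is worth making because it is nearly free.

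**What to change.** In the allocation sentences of Phase 2 Procedures and Phase 3 Procedures, add waterpipe status (current smoker or susceptible nonsmoker) to the two existing stratification factors, and state that the 1:2:2 ratio applies inside every resulting stratum. Stating that each population is randomised separately, with the existing two factors as strata, is equivalent. In the statistical section, specify the Phase 3 analysis and include population as a term in it.

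The cost is one more branching variable in the randomiser. Waterpipe status is an eligibility criterion, so it is known before allocation. The strata rise from 4 to 8, which in Phase 3 is about 200/8 = 25 people each if evenly spread. No sample size, assessment or intervention changes.

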Total Participant Accrual:

3,000

Duration of Accrual:

6 months

Duration of Study:

16 months

Sample Size (power calculations) and statistical considerations:

Power calculations were conducted on factorial MANOVAs for H2A and H2B, and general linear models for H3 (mediation). There are no established programs to calculate required sample size for multiple mediations; however, general linear models are the core procedures for multiple mediations. As stated, the factorial design is incomplete; to be conservative, this power analysis was based on a complete 3 (study arms) x 4 (health domains) x 6 (ad themes) X 2 (populations) design. Using G*Power¹⁰⁹ the required total N for detecting an effect size (small: $f = 0.10$ or $f^2 = 0.02$; medium: $f = 0.25$ or $f^2 = 0.15$; large: $f = 0.40$ or $f^2 = 0.35$) with 90% power, two-tailed, with $\alpha = .01$ for all main and interaction effects is 3934 for small, 657 for medium, and 289 for large effects. We are well-powered to detect moderate effect sizes.

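### Does quoting one set of required sample sizes for two unequal effect-size scales (f and f-squared) undermine the power statement?

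*Combined protocol and SAP*

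**What the plan says.** The section on sample size and statistical considerations opens by naming two kinds of model: "Power calculations were conducted on factorial MANOVAs for H2A and H2B, and general linear models for H3 (mediation". It treats the linear model as a stand-in for mediation because no established program sizes multiple mediation directly. It then says that "to be conservative, this power analysis was based on a complete 3 (study arms) x 4 (health domains) x 6 (ad themes) X 2 (populations)" was the layout used, and it acknowledges that the real factorial is incomplete.

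Effect sizes are given in pairs: "small: $f = 0.10$ or $f^2 = 0.02$; medium: $f = 0.25$ or $f^2 = 0.15", and 0.40 paired with 0.35 for large. The test conditions are "with 90% power, two-tailed, with $\alpha = .01$ for all main and interaction effects". The result is one N per label: "for all main and interaction effects is 3934 for small, 657 for medium, and 289 for large effects". The only conclusion drawn is that the study has ample power for moderate effects.

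The same section runs H3 separately, "to test multiple mediation effects in each study population". The enrolment section sets each population at 1000, or 2000 in Phase 2. Allocation is "randomized in a 1:2:2 ratio to one of three arms", and the arm descriptions give 200, 400 and 400 per population.

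**The concern.** Read literally, the pairs assert that f = 0.10 is the same as f² = 0.02, and so on. They are not the same: 0.02, 0.15 and 0.35 correspond to f of about 0.141, 0.387 and 0.592. One N cannot be the exact requirement for both members of a pair.

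The difference looks material at the small-effect label. With 2000 participants, a 30-df test has about 43% power at f = 0.10 and about 90% at f² = 0.02. A reader could conclude from one scale that small effects are covered and from the other that they are not.

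H3 adds to this. The section says power was worked out for it, yet prints no N, number of predictors or tested df. If the f-squared values were meant for H3, the Ns beside them appear to belong to another model.

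**Working it through.** **Inputs.** All come from the sample-size section unless noted: alpha .01; power .90; layout 3 × 4 × 6 × 2; f = 0.10, 0.25, 0.40; f² = 0.02, 0.15, 0.35; stated Ns 3934, 657, 289. Planned N is 1000 per population and 2000 in total (enrolment section). The tested df for H3 is not given, so a range of 1 to 30 is assumed.

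**Step 1: reproduce the printed Ns.** The fixed-effects F test has noncentrality λ = N·f², numerator df u and denominator df N − cells.
- Cells = 3 × 4 × 6 × 2 = 144.
- The largest interaction has u = (3−1)(4−1)(6−1)(2−1) = 30.
- The smallest N with power of at least .90 at f = 0.10, 0.25, 0.40 is **3934, 657, 289**. All three match exactly, with power .900, .900 and .902.
- As a contrast, a 15-df term in the same layout gives 3089, 513, 229.

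The Ns are therefore univariate F-test Ns for the 30-df terms, on the f scale.

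**Step 2: put the second scale into the same test.** Squaring f gives 0.01, 0.0625, 0.16, against the printed 0.02, 0.15, 0.35. With λ = N × (0.02, 0.15, 0.35), u = 30 and 144 cells, the required N is **1981, 303, 186**. Each is below its printed counterpart: 1981/3934 = 0.50, 303/657 = 0.46, 186/289 = 0.64. Reading the printed Ns on f-squared overstates the requirement by this test; it never understates it.

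**Step 3: test the plan's conclusion on both scales.** For the medium label, 657 (f) or 303 (f²) is required and 2000 are planned. Power at 2000 for the 30-df test exceeds .999 on either scale.

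**Step 4: H3 at 1000 per population.** For a regression F test with u tested predictors, λ = N·f² and denominator df = N − u − 1:

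| u (assumed) | N at f² = 0.02 | N at f² = 0.15 | Power at N = 1000, f² = 0.02 |
|---|---|---|---|
| 1 | 748 | 103 | .971 |
| 2 | 876 | 121 | .941 |
| 3 | 969 | 135 | .912 |
| 5 | 1109 | 155 | .855 |
| 10 | 1361 | 192 | .728 |
| 30 | 1980 | 287 | .424 |

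At f² = 0.15, power at 1000 is above .999 in every row. Warning domain exists only in the two warning arms, 400 + 400 = 800 per population. A 3-df domain test there has .81 power at f² = 0.02 and above .999 at f² = 0.15.

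**Step 5: is the 30-df basis hidden?** The text gives the full layout and says the Ns serve every main effect and interaction. A single N that covers all of them must be the one for the term with the most df. The real design has (6 + 24 + 24) × 2 = 108 cells and interactions of at most 3 × 5 = 15 df, for which 3088, 511 and 220 suffice. Calling the complete layout conservative is therefore correct.

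**The case for a change.** The best case for a change is that the section says a power calculation was done for H3 and then shows only the ANOVA result. Reading the pairs as one benchmark per model family makes the gap plainer, since the f-squared values then have no N of their own. Whether 1000 per population covers a small H3 effect depends on the tested df, as Step 4 shows, and the plan does not give it. A rewrite would cost one paragraph.

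The reporting gap is real. It would matter if the plan relied on small-effect power, but it does not: it prints 3934 for a small effect against 2000 planned and claims only moderate effects. The 43% and 90% figures compare two different effect sizes for a claim that is not made.

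An added H3 line could also mislead. Quoting 748, or 97% power at 1000, presents the most favourable case of a single coefficient. The plan describes multi-category predictors such as warning domain, and a 3-df test needs 969. None of these F-test figures is power for an indirect effect, which is what H3 examines, and the section already says that no established program provides that.

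**Conclusion.** The concern does not call for a change. The arithmetic observation is right: the paired values differ, the Ns come from f only, and H3 has no printed N. But the section introduces two model families just before the pairs, so the pairs are best read as the usual benchmark for each family rather than as an identity. On that reading every printed N is correct for the factorial tests and, by the same test on f-squared, larger than needed by a factor of about 1.6 to 2.2 (289/186 to 657/303).

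The one conclusion drawn, adequate power for moderate effects, holds with wide margin: 657 or 303 required against 2000, and 103 to 287 against 1000 per population for H3 over 1 to 30 tested df. An analyst needs nothing further from this paragraph to run the H2 or H3 analyses.

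This rests on univariate F tests at .01 and on an assumed range of tested df for H3, and it does not extend to power for the mediated effect. Null findings for small effects, interactions especially, should be read with that limit in mind; the printed 3934 against 2000 planned already signals it.

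### The 90% power at .01 stated for contrasts rests on one 30-df omnibus calculation; it holds for main effects and overall arm contrasts at medium effects, but not for many contrasts inside interactions

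*Combined protocol and SAP*

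**What the plan says.** All of this is in the combined protocol and SAP. Under Sample Size (power calculations) and statistical considerations, the plan admits that the factorial design is incomplete and describes its approach as a conservative choice: "this power analysis was based on a complete 3 (study arms) x 4 (health domains) x 6 (ad themes) X 2 (populations) design". At 90% power and two-tailed alpha .01, the required total N "is 3934 for small, 657 for medium, and 289 for large effects", given as one row for every main effect and interaction. It concludes: "We are well-powered to detect moderate effect sizes".

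The next paragraph widens the claim: "We will use 90% power at .01 level of significance (two-tailed) for univariate tests and contrasts". Univariate tests at .01 follow "if the omnibus multivariate test is significant at a .05 level, rather than .01, for the primary outcomes". They compare arms, domains, themes and populations, and cover the interactions of these. The plan notes the empty cells and handles them with Type IV sums of squares. It shows no calculation for a contrast and gives no contrast effect size or SD.

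Phase 2 Procedures sets 1000 smokers and 1000 susceptible nonsmokers, allocated 1:2:2, so 200/400/400 per population. For the control arm it prints "They will not receive any warnings. (N ≈ 33 per cell". For each warning arm it says "there are 24 main cells (N ≈ 32 per cell combining populations".

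**The concern.** A sample size for an omnibus F test does not carry over to a comparison of two subgroups. The omnibus test uses all 2000 people; a contrast inside an interaction may use 200, 67 or 33. The sentence on contrasts sets no limit, and Aim 2 includes exploring domain, theme and population, so readers will look at such contrasts. A non-significant one could then be taken as evidence against a moderate effect when the trial had little chance of detecting it.

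The single row also undersells the trial. It implies that 3934 people are needed for any small effect, although the arm main effect is adequately powered for a small effect at 2000.

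**Working it through.** **1. Reproducing the plan's figures.** Inputs from the sample-size section: f = 0.10, 0.25, 0.40; alpha .01; power .90; 3 × 4 × 6 × 2 = 144 cells. The highest-order interaction of that complete design has 2 × 3 × 5 × 1 = 30 df. With a noncentral F test, λ = f²N, df1 = 30 and df2 = N − 144, the smallest N are 3934, 657 and 289, an exact match. None of the other numerator df, cell counts and alphas tried gave all three. (The plan prints "medium: $f = 0.25$ or $f^2 = 0.15", but 0.25² = 0.0625; its Ns follow f.)

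**2. What the design contains.** The control arm has 6 themes × 2 populations = 12 cells. The warning arms have 2 × 4 × 6 × 2 = 96. Total filled: 108. The largest estimable interaction has 1 × 3 × 5 × 1 = 15 df and exists only among the 1,600 warning-arm participants. With 144 cells, 15 df needs 3089, 513 and 229, fewer than the plan states.

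**3. Omnibus power at the planned size.** At f = 0.25 and N = 2000, power exceeds 99.9% for every df from 1 to 30. At f = 0.10:

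| Effect | df | N available | Power |
|---|---|---|---|
| Arm | 2 | 2,000 | 94% |
| Theme | 5 | 2,000 | 86% |
| Domain | 3 | 1,600 | 82% |
| Largest interaction | 15 | 1,600 | 47% |

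For 90% power at f = 0.10, the 15-df term needs 3,088 in the warning arms, or 3,088/0.8 = 3,860 in total.

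**4. Contrasts.** The standardised difference d = 0.5 (SD 1) is an assumption: the two-equal-group equivalent of f = 0.25. SE = √(1/n1 + 1/n2); power = Φ(0.5/SE − 2.576); 90%-detectable d = (2.576 + 1.282) × SE. Example, 33.3 v 33.3: SE = √(2/33.3) = 0.245; 0.5/0.245 − 2.576 = −0.53, power 30%; detectable d = 3.858 × 0.245 = 0.95.

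| Contrast | n1 v n2 | Power at d = 0.5 | 90%-detectable d |
|---|---|---|---|
| Population | 1000 v 1000 | >99% | 0.17 |
| Text v text + graphic | 800 v 800 | >99% | 0.19 |
| Control v one warning arm | 400 v 800 | >99% | 0.24 |
| Two domains | 400 v 400 | >99% | 0.27 |
| Two themes | 333 v 333 | >99% | 0.30 |
| Text v text + graphic in a domain, pooled | 200 v 200 | 99% | 0.39 |
| Text v text + graphic in a theme, pooled | 133 v 133 | 93% | 0.47 |
| Two domains in one arm and population | 100 v 100 | 83% | 0.55 |
| Control v text in a theme, pooled | 67 v 133 | 78% | 0.58 |
| Control v text in a theme, one population | 33 v 67 | 41% | 0.82 |
| Two domain-by-theme cells, pooled | 33 v 33 | 30% | 0.95 |
| Two domain-by-theme cells, one population | 17 v 17 | 13% | 1.34 |

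At d = 0.5, 90% power needs 120 per group.

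**5. Cell sizes.** The printed control figure is one population: 200/6 = 33.3. The printed warning figure combines both, and 800/24 = 33.3 rather than 32. On one basis, pooled: control 400/6 = 67, warning 33. Per population: control 33, warning 400/24 = 17.

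**The case against.** The plan discloses that it used a complete design, calls this conservative, and is right for omnibus tests: 30 df gives a larger N than any effect the design can hold. A reader might infer from the impossible 30-df term that the moderate-effects statement is wrong or the trial too small. The documents do not support that, since step 3 shows ample power at f = 0.25.

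The list of univariate tests can also be read as F tests of interactions. It names no cell-by-cell or per-population within-theme comparison, and Aim 2 describes domain, theme and population as explored. This stands as a reason not to demand 90% for 17 v 17. It does not rescue a sentence that includes contrasts without limit.

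The effect-size translation can be disputed. For 1:2 groups, f = 0.25 means d = 0.25/√(1/3 × 2/3) = 0.53, which raises control versus text within a theme to 83% pooled and 47% per population; both still miss 90%. Spread over all 2000 people, a 0.5 SD difference between two 33-person cells is only f = √(0.5²/(0.06 × 2000)) = 0.046, below the plan's small effect. But holding f = 0.25 on that scale would require d = 0.25 × √2000 × 0.245 = 2.7 between the cells, which is hardly moderate. The plan needs to say which scale it means.

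The cell-size point is editorial. The warning-arm figure is labelled as combining populations and the control figure stands beside its N of 200, so nothing suggests concealment.

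**Conclusion.** The concern holds in a limited form. The 90% figure at .01 is supported for omnibus, main-effect and overall arm tests at medium effects. It is not shown for contrasts within interactions, and at d = 0.5 many miss it, some by a wide margin.

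A reader might take 13% to 83% as the range for all such contrasts. It is not: pooled text versus text + graphic passes within a theme and within a domain. At the other extreme, a 0.5 SD difference of differences (control versus text, between two themes and between populations) has about 8% power: SE = √(4 × (1/33.3 + 1/66.7)) = 0.42.

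The percentages rest on d = 0.5, full Phase 2 enrolment with equal splits, a normal approximation (within 2 points of the noncentral t where checked), and the .01 test alone without the multivariate gate. The 30-df reproduction, the 108-cell count and the cell sizes do not depend on d.

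**What to change.** - Limit the 90% statement to omnibus, main-effect and overall arm tests at medium effects.
- Replace the single row of Ns with figures for effects the design contains: the 90%-detectable d at .01 for each main-effect contrast and for the within-domain, within-theme and cell contrasts (last column of the contrast table), stating the SD assumption.
- For small effects, give the four power figures in step 3 with the N each uses.
- State that contrasts within interactions are exploratory and will be reported as estimates with confidence intervals.
- Print control and warning cell sizes on one basis, pooled and per population, as in step 5.

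The cost is rewording the power text and correcting two cell counts. No participants are added and the randomisation is unchanged. The stated power becomes less favourable for some contrasts, and more favourable for main effects at small effect sizes than the present row implies.
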